3.3.6. Presentations by Study Visit

When data are collected serially over time, individual data presentations may include by-visit displays. For these presentations, visits will be presented according to the nominal visit as obtained from the CRF or laboratory data. If assessments are collected with multiple dates or times within a given visit, the result closest to the scheduled visit date will be used for summary presentations. If two measurements have the same distance to the expected date, the earlier value will be used. If a subject has multiple non-missing values on the same date, then the last one is used, as determined by the time collected, if available.

3.3.7. Definitions and Terminology

Baseline Value

For purposes of analysis, the baseline value is defined as the last non-missing value obtained prior to administration of the first dose of double-masked study drug.

Day 1

Day 1 is the day/time that the double-masked study drug is first initiated.

Study Day

Study Day is defined relative to Day 1.

For events occurring prior to Day 1, the study day is calculated as:

Study Day = event date - date of Day 1.

For events occurring after Day 1, the study day is calculated as:

Study Day = event date - date of Day 1 + 1.

Study Visit

Study Visit is the nominal visit as recorded on the CRF.

Change from Baseline

Change from baseline for a given endpoint is defined as the Study Day X value minus the Baseline Value.

Adverse Event (AE)

An adverse event is any untoward medical occurrence in a subject or clinical investigation subject administered a pharmaceutical product; which does not necessarily have a causal relationship with this treatment. All adverse events will be recorded on the Adverse Event CRF.

Treatment-emergent Adverse Event (TEAE) for Placebo Run-in Period

During the placebo run-in period, a treatment-emergent AE (TEAE) is an AE that either commenced following initiation of the placebo run-in period study treatment or was present prior to study treatment but increased in frequency or severity following initiation of study treatment.

Additionally, it is assumed that an AE which was reported to have started on Day -14 (start of placebo run-in period) without an associated onset time occurred after the initiation of study treatment and is therefore a treatment-emergent adverse event (TEAE).

Treatment-emergent Adverse Event for Double-masked Period

During the double-masked period, a treatment-emergent AE is an AE that either commenced following initiation of the double-masked period study treatment or was present prior to study treatment but increased in frequency or severity following initiation of double-masked study treatment. Additionally, it is assumed that an AE which was reported to have started on Day 1 (start of double-masked period) without an associated onset time occurred after the initiation of study treatment and is therefore a treatment-emergent adverse event. AEs reported without an onset date are also assumed to be TEAEs.

Treatment-related Adverse Event

A Treatment-related AE is any adverse event reported on the CRF that is marked as being Related or Possibly Related to the study medication. Additionally, it is assumed that an AE without a relationship is a Treatment-related AE.

Concomitant Medications for Placebo Run-in Period

Concomitant medications for the placebo run-in period are those medications taken during the placebo run-in period.

Concomitant Medications for Double-Masked Period

Concomitant medications for the double-masked period are those medications taken while on the double-masked period study treatment.

Previous Medications for Placebo Run-in Period

Previous medications for the placebo run-in period are those medications that ended prior to the initiation of the placebo run-in period study treatment.

Previous Medications for Double-Masked Period

Previous medications for the double-masked period are those medications that ended prior to the initiation of the double-masked period study treatment.

Study Eye

If a subject has only one qualifying eye, that eye will be the Study Eye. If both eyes of the subject qualify, then the Study Eye will be the eye with the highest total corneal staining score. If the scores for total corneal staining are the same, the Study Eye will be the right eye.

3.4. TIMING OF ANALYSES

A final analysis will be conducted once the last subject completes or discontinues the study and the resulting clinical database has been cleaned, quality checked, and locked. This analysis may exclude the biomarker data. The analysis of the biomarker data will be conducted once the final biomarker data are available.

CONFIDENTIAL Page 13 08 August 2017

4. ANALYSIS POPULATIONS

The populations for analysis will include the modified Intent-to-Treat Population (mITT), Safety Population, and Run-in Population.

4.1. MODIFIED INTENT-TO-TREAT (MITT) POPULATION

The modified Intent-to-Treat Population (mITT) will include all randomized subjects who have at least a baseline and one post-baseline SANDE part 1 assessment. This is the primary population for efficacy analyses and subjects will be analyzed based on their randomized treatment

4.2. SAFETY POPULATION

The Safety Population will include all subjects who receive at least one dose of double-masked study medication in either eye. All safety analyses for the double-masked portion of the study will be conducted on the Safety Population, analyzed as treated.

4.3. RUN-IN POPULATION

The Run-in Population will include all subjects who receive at least one dose of single-masked placebo in either eye during the run-in period. Safety analyses for the single-masked portion of the study will be conducted on the Run-in Population.

5. STATISTICAL METHODS

Descriptive statistical methods will be used to summarize the data from this study. Unless stated otherwise, the term "descriptive statistics" refers to number of subjects (n), mean, median, standard deviation (SD), minimum and maximum for continuous data and frequencies and percentages for categorical data. All data collected during the study will be included in data listings. Unless otherwise noted, the data will be sorted first by treatment group, subject number, and then by date within each subject number.

The term 'treatment group' refers to all subjects on the same dosing regimen. There will be 2 treatment groups in this study: 0.017% P-321 Ophthalmic Solution and placebo.

All statistical testing will be two-sided and will be performed using a significance (alpha) level of 0.05 unless otherwise stated.

The statistical analyses will be conducted with the SAS® System version 9.4 or higher. All analyses will be subject to formal verification procedures. Specifically, results will be verified utilizing

CONFIDENTIAL Page 14 08 August 2017

independent programming prior to issuance of the draft statistical report. All documents will be verified by the lead statistician to ensure accuracy and consistency of analyses.

5.1. SUBJECT DISPOSITION, DEMOGRAPHIC AND BASELINE CHARACTERISTICS

Subject disposition will be presented for all subjects. The number of subjects who completed the study and discontinued from the study will be provided. The reasons for early discontinuation at any point also will be presented by treatment group. Additionally, the number of weeks on study and study drug will be summarized for all treated subjects.

Demographic data and baseline characteristics including age, gender, race, ethnicity, and weight will be summarized by treatment group and overall using descriptive statistics.

Ocular and non-ocular medical history will be descriptively summarized, and dry eye and other ocular history including MGD, BCVA, IOP, symptoms upon entry, corneal and conjunctival staining, staining in the lid wiper region, TBUT, tear osmolarity, and Schirmer tests will be summarized by treatment group and overall using descriptive statistics. This information will be statistically compared between the two randomized treatment groups using a 2-sided Wilcoxon rank-sum test for continuous variables, a 2-sided Chi-Square Test for nominal categorical variables, or a van Elteren test for ordinal categorical variables with more than 2 levels.

5.2. EFFICACY ANALYSIS

Analyses of efficacy will be conducted using the Study Eye. For all efficacy analyses by Study Eye, a secondary analysis will be conducted using all qualifying eyes. The primary and secondary efficacy analyses will be performed on the mITT Population and presented by treatment group. The dry eye symptom questionnaires can be viewed in Appendix IV of the protocol.

5.2.1. Primary Efficacy Endpoint

The primary efficacy endpoint is the mean change from baseline to Day 29 (Visit 4) in the SANDE questionnaire global symptom score from Part 1. The primary efficacy comparison will be the mean change from baseline in the SANDE global symptom score for the 0.017% treatment arm compared to placebo.

5.2.2. Primary Efficacy Analysis

The SANDE Questionnaire Part 1 is comprised of two 100mm VAS scales. One measures frequency of symptoms from rarely (0) to all the time (100). The other measures severity of symptoms from very mild (0) to very severe (100). The global score is calculated as the square root of the product of the two measurements.

CONFIDENTIAL Page 15 08 August 2017

The SANDE Part 1 global symptom score and change from baseline will be summarized by treatment and study visit. The change from baseline at Day 29 will be assessed for differences between the 0.017% P-321 treatment group and placebo using a mixed model repeated measures analysis with fixed effects for treatment, study site, visit, and treatment by visit interaction, with the baseline value as a covariate. The following 3 covariance structures will be considered: AR(1), CS, and UN. The covariance structure with the lowest AIC will be selected. The corresponding 95% confidence interval for the difference will be presented. A secondary analysis will be performed assessing the change from baseline at Day 15 from the same mixed model repeated measures analysis.

The descriptive statistics for change from screening to baseline will be presented by treatment.

Additionally, the proportion of subjects with improvement from baseline, no change from baseline, and worsening from baseline to Day 29 will be summarized by treatment group and overall. The analysis will also be performed for Day 15.

A sensitivity analysis will be performed where missing data will be imputed using the method of multiple imputation. Multiple imputation relies on the assumption that the data are missing at random. This method of imputation produces unbiased estimators of the mean and standard error, and, as such, is preferred over single imputation methods (Dziura et al., 2013). For this method, the procedure requires production of multiple datasets containing plausible values for each missing value. Using a set of values rather than a single value better accounts for the uncertainty about the value being imputed. SAS PROC MI will be used to generate 10 possible imputed datasets. The analysis described in the previous paragraph will be performed ten times, once for each dataset. The results from the analysis from each of the 10 datasets will be combined using SAS PROC MIANALYZE to produce a single inferential result.

Mean and 95% CI for SANDE Part 1 global symptom scores will be plotted by treatment and study visit.

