11.4.2 Primary Efficacy Analysis

The mean change from baseline (Visit 2) in SANDE Part 1 global symptom score for the Study Eye after 28 days of treatment in the 0.017% P-321 and placebo arms will be analyzed via analysis of covariance (ANCOVA). The dependent variable will be the observed change from baseline to Visit 4 (Day 29) in the global symptom score from SANDE Part 1, with treatment, study site, and baseline SANDE Part 1 global score as fixed effects. A significance test of the treatment difference between the 0.017% arm and placebo will be tested at the two-sided 0.05 level and corresponding 95% confidence intervals will be calculated. The analysis will be based on the mITT population only. Details regarding the handling of missing data will be described in the SAP.

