1.1. STUDY OVERVIEW

This is a multi-center, randomized, double-masked, placebo-controlled, parallel group Phase 2b trial designed to evaluate symptoms and signs in subjects with mild to moderate dry eye disease. It is anticipated that approximately 125 subjects with dry eye will need to be screened in order to randomize about 65 subjects and complete approximately 60 subjects. Subjects who meet inclusion/exclusion criteria will be enrolled in a single-masked placebo run-in period for up to 14 days. At the end of the run-in period, eligible subjects will be randomly assigned in a double-masked fashion to receive either 0.017% P-321 Ophthalmic Solution or Placebo TID for 28 days. The study will consist of four study visits and a follow up phone call: Visit 1 (Screening Visit), Visit 2 (Randomization and Treatment Day 1), Visit 3 (Treatment Day 15) and Visit 4 (Day 29, after 28 days of treatment) and a follow up phone call 5-9 days later. Three phone calls to remind subjects of dosing regimen and to inquire about adverse effects will also be done during the study and will occur between Visits 1 and 2, Visits 2 and 3, and Visits 3 and 4. The placebo-run-in is single-masked in that the subjects will remain masked to the treatment during the placebo run-in. However, the treatment is known to the investigator, medical monitor, study site personnel, and those involved in the conduct of the study. The randomized treatment assignments are double-masked in that the treatment will be masked to the investigator, medical monitor, study site personnel, subjects in the study and those involved in the conduct of the study.

This study is designed to evaluate the changes in symptoms and signs of dry eye disease including conjunctival staining of the lid wiper area of the upper eyelid (with photographs if technology is available), corneal staining, bulbar conjunctival staining, and tear break-up-time (TBUT). Dry eye symptom questionnaires including the Symptom Assessment in Dry Eye questionnaire (SANDE), the Standard Patient Evaluation of Eye Dryness (SPEED) questionnaire, and a 7-item symptom questionnaire will be completed at each visit prior to other assessments. Exploratory assessments of expression of biomarkers of inflammation in the tears and from impression cytology samples collected from the lid wiper and the bulbar conjunctiva will be performed.

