3.1. SAMPLE SIZE AND POWER

A sample size of approximately 65 randomized subjects is proposed. Assuming a dropout rate prior to Visit 3 of 10%, this provides approximately 60 subjects with post-baseline data. The sample size estimation was based on assumptions about the standard deviation and treatment effect for the change from baseline SANDE global score (Part 2 assessment) from a previous study, protocol P-321-101. At Day 28, the pooled standard deviation for the change from baseline was 22 and the difference in means was 20, representing a standard effect size of 0.9. If the true standard deviation is 22, a sample size of 30 subjects per group will provide at least 90% power to detect a true difference in means of 20 using a two-sided hypothesis test with Type 1 error of 5%. All else being equal, this sample size provides at least 70% power if the treatment difference is at least 15 units or if the standard deviation is no more than 29.

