3.3.4. Missing Data and Outliers

Every effort will be made to obtain required data at each scheduled evaluation from all subjects. See section 3.3.5 for details of imputing missing dates. A sensitivity analysis will be performed for the primary endpoint imputing missing data by multiple imputation. See section 5.2.1 for details. Unless otherwise specified, other missing data will not be imputed.

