10. PROPOSED TABLES, LISTINGS, AND FIGURES

Summary Tables

Accountabili	ty and Baseline Characteristics
14.1.1	Subject Disposition (All Subjects Enrolled)
14.1.2.1	Demographics and Baseline Characteristics (All Subjects Enrolled)
14.1.2.2	Dry Eye Assessments at Screening (All Subjects Enrolled)
14.1.3	Study Drug Exposure (All Subjects Treated)
14.1.4.1	Concomitant Medications for Double-Masked Period by Generic Name and Drug
	Classification (Safety Population)
14.1.4.2	Concomitant Medications for Placebo Run-in Period by Generic Name and Drug
	Classification (Run-in Population)
Efficacy (all a	analyses on mITT population)
14.2.1.1	Summary of SANDE Questionnaire Part 1 Global Symptom Score
14.2.2.1.1	Summary of SPEED Questionnaire Total Symptom Score
14.2.2.2	Summary of SPEED Questionnaire Type of Symptom Experience and When
	Symptoms Occur
14.2.3.1.1	Summary of 7-item Symptom Questionnaire Score – Eye Dryness
14.2.3.2.1	Summary of 7-item Symptom Questionnaire Score – Burning/Stinging
14.2.3.3.1	Summary of 7-item Symptom Questionnaire Score – Photophobia
14.2.3.4.1	Summary of 7-item Symptom Questionnaire Score – Foreign Body Sensation
14.2.3.5.1	Summary of 7-item Symptom Questionnaire Score – Blurred Vision
14.2.3.6.1	Summary of 7-item Symptom Questionnaire Score – Itching
14.2.3.7.1	Summary of 7-item Symptom Questionnaire Score – Pain
14.2.4.1.1	Summary of Staining of the Lid Wiper Area – Study Eye
14.2.4.2	Summary of Staining of the Lid Wiper Area – All Qualifying Eyes
14.2.4.3	Summary of Fluorescein Score – Study Eye
14.2.4.4	Summary of Fluorescein Score – All Qualifying Eyes
14.2.4.5	Summary of Lissamine Score – Study Eye
14.2.4.6	Summary of Lissamine Score – All Qualifying Eyes
14.2.5.1.1	Summary of Bulbar Conjunctival Staining Total Score – Study Eye
14.2.5.2	Summary of Bulbar Conjunctival Staining Total Score – All Qualifying Eyes
14.2.5.3	Summary of Bulbar Conjunctival Inferior Nasal Region Score – Study Eye
14.2.5.4	Summary of Bulbar Conjunctival Inferior Nasal Region Score - All
	Qualifying Eyes
14.2.6.1.1	Summary of Corneal Staining Total Score – Study Eye
14.2.6.2	Summary of Corneal Staining Total Score – All Qualifying Eyes
14.2.6.3	Summary of Corneal Staining Inferior Region Score – Study Eye
14.2.6.4	Summary of Corneal Staining Inferior Region Score – All Qualifying Eyes
14.2.7.1.1	Summary of Tear Breakup Time (TBUT) – Study Eye
14.2.7.2	Summary of Tear Breakup Time (TBUT) – All Qualifying Eyes

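### The only sensitivity analysis planned for missing primary-endpoint data makes the same missing-at-random assumption as the primary model, so it cannot show the effect of missing scores that are worse than the observed data predict

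*SAP*

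**What the plan says.** The protocol leaves missing data to the SAP (Protocol 11.4.2 and 11.6). SAP 3.3.4 answers for the primary endpoint: "A sensitivity analysis will be performed for the primary endpoint imputing missing data by multiple imputation". It imputes no other missing data unless a section says so. SAP 5.2.2 gives the method: ten PROC MI datasets, each analysed as in the main analysis and combined with PROC MIANALYZE. It states the assumption openly: "Multiple imputation relies on the assumption that the data are missing at random". It has no delta-adjusted, tipping-point or reference-based step. (SAP 3.3.4 points to 5.2.1 for these details; they are in 5.2.2.)

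The imputation paragraph does not name its population. Three places point to mITT:

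- SAP 5.2: "The primary and secondary efficacy analyses will be performed on the mITT Population and presented by treatment group".
- The efficacy table heading in SAP 10: "analyses on mITT population".
- Protocol 11.4.2, written for an ANCOVA: "The analysis will be based on the mITT population only".

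Under SAP 4.1 the mITT population "will include all randomized subjects who have at least a baseline and one post-baseline SANDE part 1 assessment". The first scheduled post-baseline SANDE Part 1 is at Visit 3.

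On expected loss, SAP 3.1 says: "Assuming a dropout rate prior to Visit 3 of 10%, this provides approximately 60 subjects with post-baseline data". SAP 1.1 expects to "randomize about 65 subjects and complete approximately 60 subjects".

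**The concern.** A sensitivity analysis is informative when it changes the assumption that might be wrong. Here the main analysis and the check share it. Missing at random is the condition under which a likelihood-based mixed model is valid; that is a property of the method, and the SAP does not state it for the mixed model. If subjects with missing scores did worse than their observed data predict, both analyses miss it in the same way.

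The population narrows the check further. About 60 subjects are expected to have post-baseline data and about 60 to complete. On these rounded figures nearly all expected loss comes before Visit 3, and imputation within mITT would have little to fill. The subjects lost early would be in neither analysis.

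Whether any of them have a usable score is unclear. Protocol 9.1 includes Early Termination among the symptom assessments, but the procedure list in Protocol 7.9 and both schedules (Protocol Appendix I, SAP 1.2) do not. These passages must be reconciled.

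At stake is the reading of a modest positive result: if it depended on the assumption, no planned analysis of the primary endpoint would show it.

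**Working it through.** **The plan's own figures.** With 30 per group and two-sided alpha 0.05, power by the noncentral t is 93.3% for difference 20 and SD 22, 73.8% for 15 and 22, and 74.8% for 20 and 29. The SAP's statements of at least 90% and at least 70% hold.

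**Both analyses miss the same departure.** In a large-sample simulation the active change was -20 under missing at random, 10% of active Day 29 scores were missing, and the two post-baseline visits had correlation 0.5 (an assumption). When the missing scores were worse by 10, 20 or 30 mm, the true mean moved to about -19, -18 and -17. The missing-at-random estimate and the ten-dataset imputation estimate both stayed at about -20.0.

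**Subjects outside mITT.** 65 - 60 = 5, or 0.10 x 65 = 6.5, assuming no Early Termination SANDE Part 1 score.

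**Effect on the result.** Assumptions:

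- SD 22. SAP 3.1 takes it from SANDE Part 2, whereas the primary endpoint is Part 1.
- 10% loss in each arm, with lost active subjects at the placebo mean.
- Imputed subjects counted as if observed, and no baseline or site adjustment.

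Steps:

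1. mITT, 65 x 0.9 / 2 = 29.25 per arm: SE = 22 x sqrt(2/29.25) = 5.75; t(56.5) = 2.003; threshold 11.5.
2. All randomized, 33 and 32: SE = 22 x sqrt(1/33 + 1/32) = 5.458; t(63) = 1.998; threshold 10.91.
3. Difference in all randomized = mITT difference x (1 - share of the active arm lost).

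| mITT difference | mITT p | All-randomized difference | p |
|---|---|---|---|
| 20 | 0.001 | 20 x 0.9 = 18.0 | 0.002 |
| 15 | 0.012 | 15 x 0.9 = 13.5 | 0.016 |
| 12 | 0.042 | 12 x 0.9 = 10.8 | 0.052 |

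4. Upper end of the fragile band: 10.91 / 0.9 = 12.1. mITT differences from about 11.5 to 12.1 (p from 0.050 to 0.040) lose significance.
5. Share of significant mITT results in that band, P(11.52 < d < 12.12) / P(d > 11.52) with SE 5.75: 1.6%, 4.9% and 7.8% for true effects of 20, 15 and 12.

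**Range.** With 5 of 65 lost evenly, 12 becomes 11.1 (p=0.047) and stays significant. If all 6.5 were active subjects (6.5/32.5 = 20%), 15 becomes 12.0 (p=0.032) and 12 becomes 9.6 (p=0.083).

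**Tipping shift.** With 10% of active scores missing and only those shifted, the shift that removes significance is (difference - 11.52) / 0.10: about 5 mm for 12, 35 mm for 15 and 85 mm for 20.

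**Trial-level simulation.** Settings: 1,500 trials each, 33/32 subjects, 7 sites, residual SD 22, within-subject correlation 0.6, and 3 subjects per arm lost at random before Visit 3. The table shows the share of mITT-significant trials that lose significance.

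| Imputation | True 20 | True 15 | True 12 |
|---|---|---|---|
| Jump-to-reference, all randomized | 4.7% | 10.9% | 18.0% |
| Missing at random, all randomized | 1.2% | 3.2% | 6.0% |
| Missing at random, mITT | 0% | 0% | 0% |

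**The case against.** **Missing-at-random methods already handle many poor outcomes.** A reader might infer that the plan ignores subjects who did badly and then left. The documents do not support that. A poor observed Day 15 score informs both the mixed model and the imputation. What is untested is an outcome worse than the observed data predict, and subjects lost before Visit 3 have only baseline data to predict from.

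**The simulated reversal rates might be read as evidence that the plan is biased.** They are not. Loss in those trials was at random, so the mITT mixed model was unbiased. The reversals show how conservative jump-to-reference is, plus imputation variance. Missing-at-random imputation in all randomized subjects accounts for 1.2, 3.2 and 6.0 points, leaving about 3.5, 7.7 and 12.0 for jump-to-reference. The 0% in mITT arises because no value is missing there.

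**There is a check that departs from missing at random.** SAP 5.2.4 item 9 counts missing as non-response, using the same SANDE Part 1 global score. This stands as partial mitigation, but it concerns a secondary binary endpoint and is also an mITT analysis.

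**The early-loss argument rests on inference.** The imputation population is inferred, and the timing of loss is read from two approximate figures. If Early Termination scores are collected as Protocol 9.1 indicates, some early dropouts enter mITT and the planned imputation has more to do. This limits confidence in the size of the problem. It does not remove the shared assumption.

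**The trial is a 28-day Phase 2b study of 65 subjects.** That supports treating the point as a cheap improvement and not as a defect that puts the primary analysis in question.

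**Conclusion.** The point holds: for the primary endpoint, no planned analysis departs from missing at random, and subjects lost before Visit 3 probably enter no analysis of it.

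The size is small. At the plan's differences of 20 and 15 the conclusion survives even loss, and 15 also survives loss confined to the active arm. Under 10% even loss only a narrow band of mITT results is fragile. This depends on the SD from SANDE Part 2 carrying over to Part 1, on lost active subjects having the placebo mean, and on counting imputed values as observed.

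A reader might go further and infer that the primary result is biased in favour of the drug. The documents give no dropout by arm or by reason, so neither the direction nor the size of any departure can be assumed.

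**What to change.** Keep the mITT mixed model as primary. Keep the current imputation and name its population. Add to SAP 5.2.2:

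> A further sensitivity analysis will include all randomized subjects. Missing Day 15 and Day 29 SANDE Part 1 global scores will be imputed by jump-to-reference: after the last observed visit, active-arm means are set to the placebo-arm visit means, and any observed Day 15 residual is taken from the subject's own randomized-arm mean, with placebo-arm covariance and adjustment for baseline and site. Each imputed dataset will be analysed with the primary mixed model by randomized arm and combined with PROC MIANALYZE.

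A delta-adjusted tipping-point analysis is an acceptable alternative if it is also run in all randomized subjects. Once Protocol 9.1, Protocol 7.9 and the two schedules are reconciled, state how any Early Termination SANDE Part 1 score is used.

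The analysis is feasible because Protocol 6.3, criterion 2, requires Visit 2 SANDE Part 1 scores before randomization. It should be written before unmasking, since it would otherwise be post hoc.

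The cost is one paragraph, one modified imputation step and one table, with no change to the primary analysis or sample size. The downside is extra programming and a somewhat smaller, conservative estimate, because jump-to-reference assumes that lost active subjects keep no benefit.
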